Children with Attention-Deficit/Hyperactivity Disorder (ADHD) are typically treated with two types of medications with differing mechanisms of action: stimulants and non-stimulants. The stimulant Vyvanse (lisdexamfetamine, LDX), and the non-stimulant Intuniv (extended-release guanficine, GXR), are both FDA-approved treatments for ADHD in children. Clinical trials have shown that both medications are effective in reducing ADHD symptoms, although the neurobiological mechanisms by which Vyvanse and Intuniv produce these effects remain unknown. The aim of this study is to examine the mechanisms by which LDX and GXR reduce symptoms in children with ADHD. MRI scanning will be used to understand the structure and blood flow within the brains of children with ADHD treated with LDX and GXR.

A total of thirty (30) children with ADHD and ten (10) age- and sex-matched, healthy controls will be scanned at the beginning of the study. In this first part of the study, MRI findings will be compared between the groups (i.e., children with and without ADHD) to see whether brain functioning of children with ADHD differs from that of healthy children. In the second part of the study, the children with ADHD will be randomized (1:1 ratio) to receive treatment with LDX or GXR for six (6) weeks. In the first few visits of the treatment phase of the study, the study doctor may adjust the medication dose to optimize its effect. At the end of the study, the children with ADHD treated with LDX or GXR will have a second MRI scan. The findings of that second MRI scan will be compared to the first MRI scan in order to identify brain changes due to the medication. These second MRI scans will also be compared to the scans of the healthy controls.

We seek to examine whether treatment with LDX and GXR leads to changes in brain structure and function and thereby help to reduce symptoms of ADHD. Furthermore, we will examine how these two drugs differ in yielding their therapeutic effect. This may inform how specific changes in the brain may underlie improvement in the various symptoms of ADHD.

Background, Significance and Rationale

Background, Significance and Rationale

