Families may be approached by mental health providers and clinicians who receive information about our study through mailings and e-mails. Families may receive direct mailings about our research study.

Families may also be approached by our research staff directly if our staff receive permission to distribute study information at community events and groups.

How will the study be advertised/publicized?

Participants will be recruited through:

- Study recruitment websites
- Flyers and brochures posted/distributed in the community
- Direct mailings
- Advertisements placed in community/neighborhood newspapers
- Advertisements on web-based resources for parents, social media platforms, and other websites such as Google

Do you have ads/recruitment material requiring review at this time?

Yes

Does this study involve a clinical trial?

Yes

Please provide the NCT Registration Number

NCT02259517

Concurrent Research Studies

Will subjects in this study participate in or be recruited from other studies?

Yes

Describe concurrent research involvement

Protocol #7096: Umbrella Screening for Brain Imaging Studies (PI: [name])

Protocol #6573: MRI Study of Emotion and Attention (PI: [name])

Protocol #7261R (formerly 6235): Examining the Effects of Stimulant Medication on Emotional Liability in Patients with ADHD (PI: [name])

Protocol #7549: MRI Study of Youth with Anxiety (PI: [name])

Children in this study may participate in and/or be recruited from Protocol #7096, which encompasses the screening procedures for this and other research studies ongoing in this laboratory. Children with ADHD in

this study may also be recruited from Protocol #6573 (e.g., if parents express interest in medication after enrollment in #6573). Children with ADHD enrolled in Protocol #7261R will only be eligible to switch into Protocol #6961 if they have dropped out of #7261R before starting medication or if they were treated with placebo.

Healthy control data may be pooled across Protocols #6573, #7261R, and this protocol because study procedures for healthy control subjects are nearly identical across all three studies. Generally, healthy controls will NOT be scanned separately for each protocol. We may also share data collected from children with ADHD under Protocols #6573 and 7261R with data collected in this protocol.

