- **Titration of GXR:** The treating physician will dose GXR to optimize clinical response. Titration will begin at 1 mg and will advance through the dosage range (1 - 4 mg) to find the best response that provides no more than mild adverse events. Treatment response will be defined as a clinician-rated CGI-I score ≤ 2 (Improved or Very Much Improved) with no more than mild associated adverse events based on a clinical review of side effects. For children under 25 kg/55 lbs, the dose of GXR will not exceed 1 mg per day. The treating clinician will monitor heart rate and blood pressure to ensure that cardiovascular risk is minimized. Flexibility in the dosing will be up to the treating physician as long as the dosing does not go outside of the FDA approved guidelines of 1 - 4 mg daily.

- **Concomitant Medication:** The treating physician will review any potential concomitant medications, and make recommendations as clinically indicated. For example, GXR doses may be adjusted when used concomitantly with strong CYP3A4 inhibitors (e.g., boceprevir, clarithromycin) or inducers (e.g., avasimibe, carbamazepine). In clinical practice, melatonin is often used to alleviate insomnia related to ADHD medications like LDX. The treating physician will have the option of recommending melatonin 1-6 mg nightly as needed for insomnia.

See Criteria for Early Discontinuation

Follow Up Evaluation and MRI Scan

After completing the medication trial, children with ADHD will be scheduled for a follow-up evaluation. The follow-up evaluation will be similar to the baseline evaluation but shorter in length. The second MRI scan will be identical to the first MRI scan.

1. **Neuropsychological Testing:** We will repeat all neuropsychological tests with the exception of the measure of intelligence, which is not expected to change during the study period.
2. **Diagnostic Assessments:** Likewise, we will repeat all diagnostic assessments with the exception of the diagnostic interview.

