3. **Second MRI Scan:** The procedures for the second MRI scan will be identical to the first MRI scan. In summary, parents/guardians will be asked to fill out the MRI Metal Screening Questionnaire to confirm that participants do not have any MRI contraindications. Parents/guardians will be reminded to have their children dress in comfortable clothing without any metal on them. Before the MRI scan, participants will be asked to remove any jewelry, watches, etc. A metal detector will be used to confirm that participants do not have any metal on their body. Female participants who have had their first period will take a urine pregnancy test to confirm they are not pregnant. Participants with MRI contraindications will not undergo the second MRI scan.

Like the first MRI scan, the second MRI scan will last 60 to 90 minutes include anatomical, resting, diffusion tensor imaging (DTI), arterial-spin labeling (ASL), and functional pulse sequences. The functional tasks will be developmentally appropriate with respect to instructions, stimuli, etc.

Follow Up Treatment

All ADHD participants will be followed free-of-cost by the study team until an appropriate referral is secured. We will supply participants with either LDX or GXR, matching the treatment received during the clinical trial, free-of-cost for one month. After the first month, parents/guardians will have to pay for the medication. To secure timely referrals, the study team will begin arranging for follow-up care as soon as possible after ADHD participants begin the study.

Future Research

After completing the study, we may re-contact parents/guardians in order to ask them and/or their child who participated in the study about completing additional assessments. The assessments would be an extension of the baseline (healthy control participants) or follow-up evaluation (ADHD participants). For example, we may ask parents/guardians and participants to complete an additional rating scale or brief neuropsychological assessment. Only assessments listed in "Assessment Instruments" would be administered.

Likewise, after completing the study, we may contact parents/guardians about participation in future research such as ongoing or new studies in the lab. Participants and their parents/guardians will not be required to partake in future research and may decline participation when contact. Parents/guardians may withdraw their permission to be contacted at any time by contacting the research team.

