Title: An fMRI Study of Stimulant vs. Non-Stimulant Treatment of ADHD

NCT Number: NCT02259517

Document Date: July 10, 2020

Hypothesis Testing

Primary Objective: Vyvanse (lisdexamfetamine; LDX) reduces impulsivity by normalizing cognitive control and reward processing circuits, whereas Intuniv (guanfacine, extended-release; G-EX) reduces impulsivity by normalizing cognitive control but not reward processing circuits.

We will first examine whether there are significant pre- vs. post-treatment changes in cognitive control and reward processing circuits. **Task-based functional MRI (fMRI) analyses:** We will enter each participant's task-related contrast map into a 2×2 repeated measures factorial model, treating Time as a repeated measure with two levels (pre- and post-treatment), and Treatment as a between group factor with two levels (LDX and G-EX). We will isolate an interaction term (Time \times Treatment) to determine differential effects of treatment on task-related activation and then conduct post-hoc t- tests to determine the nature of the interaction. **Resting-state functional connectivity MRI (Rs-fcMRI) and Diffusion Tensor Imaging (DTI):** Analyses will be similar to those for task-based fMRI, but dependent variables will be seed based connectivity and FA maps.

For mediation analysis of treatment effects, we first estimate the changes in cognitive control and reward processing circuits that result from treatment (described in paragraph above). We then establish that the changes in these circuits, in turn, affect impulsivity, while controlling for treatment group. To estimate **path a (Fig. 1)**, we will use a linear regression model with pre-post

[figure not shown]

Figure 1 Mediation Model

changes in cognitive control and reward processing circuits as the outcome variable and treatment as the predictor variable. If we find a significant effect of treatment on both reward and cognitive control circuits, we will pursue multiple mediation analyses; otherwise, we will include only the circuit in which there is a significant effect of treatment. To estimate **path b**, we will use a linear regression model with pre-post change scores in impulsivity (based on parent report) as the outcome and

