pre-post change in cognitive control or reward processing circuits as primary predictors, while controlling for baseline impulsivity and treatment group. The mediation effect is then estimated by taking the product of the estimates for **path a and b** and using the bootstrap method to obtain standard errors, confidence intervals, and the test for statistical significance.

To test whether treatment effects on cognitive control or reward processing circuits are specific in mediating improvements in impulsivity, we will explore whether treatment-related changes in other neural networks also mediate the effect of treatment on impulsivity. We will first screen these additional neural networks based on a significant effect of treatment on connectivity within these networks. Only networks that show significant change with treatment will be added to the multiple mediation analyses described above. The indirect effects of the cognitive control or reward processing circuits will be tested in the existence of the mediation effects of other neural networks using the bootstrapping method.

Power: Power for detecting the mediation effect depends on the size of the associations between (a) treatment group and changes in cognitive control and reward processing circuits, and (b) changes in cognitive control and reward processing circuits and changes in impulsivity. Based on tabulated recommendations for sample sizes needed to test mediation effects, with a sample size of $n=60$, we have more than 80% power to detect a significant mediation effect with medium effect size of both paths a and b.

Secondary Objective: ADHD patients with baseline MRI anomalies within reward processing circuits will respond to Vyvanse, but not Intuniv, treatment. Conversely, ADHD patients with baseline MRI anomalies that are circumscribed to cognitive control circuits (i.e., reward processing comparable to healthy controls) will predict response to either Intuniv or Vyvanse.

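### Claims that both drugs act alike rest on change over time with no untreated rescan, so they cannot be read as drug effects; the randomised LDX-versus-GXR contrasts are not affected

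*Protocol*

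**What the plan says.** **Arms.** The Lay Summary has children with ADHD "randomized (1:1 ratio) to receive treatment with LDX or GXR for six (6) weeks". Randomization Procedures describes the same two open-label drugs. One paragraph differs: the tic-disorder text under the procedures for minimizing risks has a child randomised to medication or placebo. It must be reconciled with the other two sections.

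**Who is rescanned.** "After completing the medication trial, children with ADHD will be scheduled for a follow-up evaluation", and that visit includes the second scan. Controls have none. Under Future Research, later assessments would be "an extension of the baseline (healthy control participants) or follow-up evaluation (ADHD participants"). The payment caps agree: 150 + 10 = 160 dollars for a control (one visit), and 100 + 150 + 2 x 10 = 270 dollars for a child with ADHD (two visits).

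**How change is read.** The Lay Summary compares second with first scans to find changes "compared to the first MRI scan in order to identify brain changes due to the medication". The Aim speaks of changes that the two treatments produce. Hypothesis 1b expects prefrontal measures to move toward those of controls under either drug. The SAP's primary objective has LDX normalising both cognitive control and reward circuits, and GXR normalising cognitive control only. Its analysis text opens: "We will first examine whether there are significant pre- vs. post-treatment changes in cognitive control and reward processing circuits". It then specifies a 2 x 2 model, isolates Time x Treatment, and adds post-hoc t-tests.

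**The marker.** The SAP's secondary objective says that baseline anomalies confined to cognitive control circuits "will predict response to either Intuniv or Vyvanse".

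**The concern.** Randomisation between two active drugs identifies the difference between them. It does not identify what either drug does compared with no drug. A change seen in both arms may be a drug effect, but it has rivals:

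- familiarity with the scanner and the tasks on an identical second scan, mainly for task fMRI;
- natural course over the treatment period;
- for parent-rated impulsivity under open-label treatment, expectancy and regression to the mean;
- for subgroups defined by a baseline MRI anomaly, regression to the mean in the MRI measure itself.

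The planned comparison of second scans with the controls' scans does not remove these. It sets a second exposure in one group against a first exposure in the other, and the controls provide no estimate of the repeat-scan shift.

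At stake are the shared-effect conclusions: that both drugs change cognitive control circuits, and that a cognitive-control anomaly marks response to either drug. Neither document states this limitation.

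**Working it through.** The plan gives no figure on this point. Its two power statements concern mediation and moderation.

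**1. What each contrast identifies.** Let t be the mean change that would occur without any drug, and let L and G be the true effects of LDX and GXR on a circuit measure.

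- Mean change in the LDX arm: t + L
- Mean change in the GXR arm: t + G
- Time x Treatment, and path a: (t + L) - (t + G) = L - G

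The common term t cancels in the third line only. If both drugs act equally (L = G), then L - G = 0, the interaction is null and path a is zero. The evidence left is t + L in one arm and t + G in the other, and no observation in the design estimates t.

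**2. The same argument for the marker.** In the SAP's moderation model, write the slope of impulsivity change on the baseline marker as p + mL under LDX and p + mG under GXR. Here p is the slope that would exist without any drug.

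- Group x baseline: (p + mL) - (p + mG) = mL - mG, free of p
- A marker that works for either drug (mL = mG = m): shared slope p + m, with p and m inseparable

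A purely prognostic marker (m = 0) gives the same picture.

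**3. Illustration for within-arm change.** Inputs: 30 ADHD completers (Description of Subject Population) at 1:1 gives 15 per arm; two-sided 5%; no drug effect. The drift d, in SD of the change score, is an assumption. The rejection probability of a paired t-test is P(|T| > t crit), where T is noncentral t with n - 1 df and noncentrality d x sqrt(n). For n = 15, t crit = 2.145.

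| Assumed d | d x sqrt(15) | One arm of 15 | Time x Treatment, 15 per arm (simulated) |
|---|---|---|---|
| 0 | 0 | 5% | 5.0% |
| 0.1 | 0.387 | 6.5% | 5.0% |
| 0.2 | 0.775 | 11% | 5.1% |
| 0.3 | 1.162 | 19% | 5.2% |
| 0.5 | 1.936 | 44% | 4.7% |

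With 30 per arm, as the SAP's n = 60 implies, the within-arm figures for d = 0.1 to 0.5 are 8% to 75%, and the interaction stays near 5%. A larger sample does not cure the problem; it detects the drift more often.

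**4. Illustration for the marker.** The assumptions are no drug effect, a marker correlated 0.3 with baseline impulsivity, and test-retest correlation of impulsivity between 0.5 and 0.8. In simulation the slope across both arms was significant in 8% to 12% of trials at n = 30 and 10% to 21% at n = 60. Group x marker stayed at about 4% to 6%.

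**The case against.** **The SAP already tests the right thing.** Its only explicit model test is the interaction, and only circuits with a significant treatment effect go into the mediation analysis. This stands. A reader might infer that the trial's main comparison is confounded by time; step 1 shows that it is not. A reader might also take the SAP's opening sentence as a pooled pre-post test and quote a large false-positive rate for it. The SAP specifies no such test: the sentence introduces the 2 x 2 model, and the t-tests are there to explain an interaction. The table in step 3 therefore shows the behaviour of within-arm change if it is read as evidence. It is not an error rate of the plan.

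**The drift is invented.** It is assumed, and nothing shows that it would run toward controls. Hypothesis 1a expects reduced activation in ADHD, so habituation that lowered activation further would count against Hypothesis 1b. Regression to the mean is weak for whole-group MRI means, because children are not selected on MRI. Task familiarity has no obvious bearing on volumes or FA. All of this limits the likely size. It does not supply the missing reference.

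**The predicted pattern is an internal check.** A time effect that moved both circuits in both arms would contradict a GXR effect confined to cognitive control. That is a partial check. It would miss a drift confined to the cognitive-control measures.

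**The lead sentence is lay language.** That is true, but the Aim, Hypothesis 1b and the shared half of the primary objective carry the same reading.

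**Placebo data may exist elsewhere.** A reader might infer that the laboratory already holds an untreated reference, since the Protocol says "We may also share data collected from children with ADHD under Protocols #6573 and 7261R with data collected in this protocol" and lets #7261R children switch into this trial if they left before medication "or if they were treated with placebo". The documents do not support this. They do not say that those children had a second scan. They call procedures nearly identical only for healthy controls. The switching rule also means the same children could appear on both sides of the comparison.

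**Conclusion.** The point holds for the shared-effect claims and no further. Hypothesis 1b, the Lay Summary's attribution, and the statement that both drugs normalise cognitive control depend on a quantity in which drug effect and time effect are added together. The half of the secondary objective about response to either drug depends on a slope in which prognosis and drug response are added together. Both conclusions follow from the design by algebra and need no assumed drift. They do assume two active arms, as the Lay Summary, Randomization Procedures and the SAP all describe.

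The size of any bias is unknown, and the percentages are illustrations under stated assumptions. Active-only arms are a legitimate choice for comparing two drugs, and the randomised difference stands. What needs correcting is the set of conclusions the documents draw beyond that difference.

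**What to change.** 1. In the Lay Summary, the Aim, Hypothesis 1b and the SAP's primary objective, limit causal statements about the drugs to the LDX-versus-GXR difference. Report within-arm change, with its confidence interval, as change over time, and state that no untreated child is rescanned.
2. In the SAP's secondary objective, restate the either-drug half as a prognostic association: the baseline cognitive-control slope across both arms, with its confidence interval. Reserve differential prediction of drug response for the Group x baseline terms.
3. Reconcile the placebo wording in the tic-disorder paragraph with the Lay Summary and Randomization Procedures.

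The cost is wording in two documents, with no new scans, patients or arms. The continuing-review section reports enrolment as ongoing, with 38 enrolled and 24 completed, so the change can precede the final analysis. The downside is narrower claims for the shared-effect hypotheses.

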Attention deficit/hyperactivity disorder (ADHD) is associated primarily with debilitating levels of inattention, hyperactivity, and impulsivity. Psychostimulant medications such as Vyvanse (lisdexamfetamine, LDX) are the first-line treatment of ADHD; however, many children with ADHD are treated with non-stimulant medications, such as alpha-2 agonists. Extended-release guanfacine (GXR), an alpha-2 agonist, is FDA approved for the treatment of ADHD in children.

Whereas MRI studies have examined the effects of psychostimulant treatment such as LDX on the structure and function of the brain, very limited data are similarly available on GXR effects. Interestingly, whereas LDX is thought to alleviate ADHD symptoms through its effects on dopaminergic and noradrenergic pathways, alpha-2 agonists, like GXR, are specific to noradrenergic pathways.

Combining MRI with a pharmacological trial of either LDX or GXR, we aim to examine the effects these treatments, which exhibit differing mechanisms of action, on neural circuits underlying cognitive control. Our goals are to examine and compare the effects of treatment with LDX or GXR on circuit abnormalities, to test whether engagement of target neural circuits (i.e., cognitive control circuits) results in symptom reduction (i.e., reduced impulsivity), and to explore predictors of treatment response. We will examine treatment effects using multiple units of analysis (neuroimaging, clinical interviews, and self- and parent-reports).

Developing a better understanding of how existing treatments lead to symptom improvement should facilitate the development of more effective treatments with fewer side effects.

Specific Aims and Hypotheses

Specific Aims and Hypotheses

Aim: To determine and compare the changes in brain structure and function that LDX and GXR treatment produce in patients with ADHD.

Hypothesis 1a: Before treatment, ADHD participants compared with healthy controls will have (i) significantly reduced volumes in the prefrontal cortex, (ii) altered connectivity between the prefrontal cortex and basal ganglia and (iii) reduced prefrontal task-related activation (fMRI signal) on an fMRI task of impulse control.

Hypothesis 1b: Following 6 weeks of treatment with either LDX or GXR, MRI measures of the prefrontal cortex will change to become more similar to those of healthy control participants.

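### A significant mediation test cannot by itself establish that circuit change lowers impulsivity, because circuit change is not randomised and both changes cover the same pre-post interval

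*Protocol*

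**What the plan says.** The protocol (Background, Significance and Rationale) lists among its goals "to test whether engagement of target neural circuits (i.e., cognitive control circuits) results in symptom reduction (i.e., reduced impulsivity". The SAP's Primary Objective is also worded as a mechanism: each drug lowers impulsivity by normalising circuits. Its mediation section goes further: "We then establish that the changes in these circuits, in turn, affect impulsivity, while controlling for treatment group".

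The planned models are:

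- **Path a:** a linear regression with "changes in cognitive control and reward processing circuits as the outcome variable and treatment as the predictor variable".
- **Path b:** the change in parent-rated impulsivity is regressed on circuit change over the same interval, with "pre-post change in cognitive control or reward processing circuits as primary predictors, while controlling for baseline impulsivity and treatment group".
- **Test:** "The mediation effect is then estimated by taking the product of the estimates for" the two paths, with bootstrap inference. A circuit enters the mediation model only if treatment has a significant effect on it.

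On timing, the protocol (Follow Up Evaluation and MRI Scan) states: "After completing the medication trial, children with ADHD will be scheduled for a follow-up evaluation". The second scan and the repeated rating scales both belong to that evaluation. There is no scan between baseline and follow-up. Weekly clinician CGI-I ratings, and weekly parent assessments whose instrument is not named, are collected, but the mediation model does not use them.

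The SAP's one further check asks whether other networks also mediate. Neither document contains a reverse-order model, a sensitivity analysis for confounding of path b, or a caveat on causal reading.

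**The concern.** Randomisation protects path a, the LDX-versus-GXR difference in circuit change. It does not protect path b, because nobody is randomised to a circuit change. Within an arm, a correlation between the two changes can arise in three ways: the circuit drives impulsivity, impulsivity drives the circuit, or something else drives both. Since the two changes cover the same interval, their order in time is no help either.

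The protocol itself suggests how the alternatives could occur. Dose is advanced according to clinical response (Medication Management), so a child's symptom course partly determines drug exposure at the second scan. Adherence is expected to vary and is tracked against a 70% threshold (Criteria for Early Discontinuation), and it could move circuit and symptoms together. Adjusting for treatment group removes neither.

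At stake is the SAP's primary objective. A positive result could be read as showing mechanism when the circuit plays no part in symptom change.

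**Working it through.** **Inputs.** From the SAP: n=60, medium effects on both paths, bootstrap test of a × b. From the protocol (Description of Subject Population): 30 ADHD completers, so n=30 is shown too. Assumed, because the mediation section does not give them: f² = 0.15 for medium and a two-sided 5% level (both appear only under the SAP's Secondary Objective), normal errors, no dropout.

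**Step 1. The plan's own figure.** The SAP states more than 80% power. With noncentrality f² × n = 0.15 × 60 = 9, power is 0.839 for path a and 0.838 for path b. Joint significance is 0.839 × 0.838 = 0.70. Simulation of the SAP models gives 68% (percentile bootstrap) or 77% (bias-corrected). The stated figure is not reproduced under these assumptions. That is a separate matter; about 68–70% is the benchmark below.

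**Step 2. Why direction is not identified.** Let T be treatment (unit variance), M circuit change and Y impulsivity change.

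Forward model: M = aT + e₁ and Y = bM + e₂, unit error variances, a = b = 0.39 (0.39² ≈ 0.15).

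The same joint distribution is produced by a reverse model in which Y comes first:

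- drug effect on Y = ab = 0.39 × 0.39 = 0.152
- effect of Y on M: k = b/(1 + b²) = 0.39/1.152 = 0.339
- direct drug effect on M = a − k × ab = 0.39 − 0.339 × 0.152 = 0.339

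The true mediated effect through M is zero here, yet the data have the same distribution, so any test rejects at the same rate. In both models the within-arm correlation of M and Y is b/√(1 + b²) = 0.36. A common cause with standardised loading 0.6 on each variable also gives 0.6 × 0.6 = 0.36. Adding baseline impulsivity to both models leaves the argument unchanged.

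**Step 3. How often a × b is significant.** Percentile bootstrap, ranges over independent simulation runs:

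| True state | n=60 | n=30 |
|---|---|---|
| Circuit → impulsivity | 67–70% | 26–28% |
| Impulsivity → circuit, drug also moves circuit (matched) | 66–69% | 26–27% |
| Common cause, drug also moves circuit | 67–70% | 26–27% |
| Pure treatment → impulsivity → circuit chain | 13–17% | 5–6% |
| Drug moves circuit, no circuit–impulsivity link | 5% | 4% |

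The pure chain is low because path a shrinks to 0.39 × 0.39 = 0.152, with f² = 0.152²/1.152 = 0.020. Power for path a at n=60 is then 0.19, and 0.19 × 0.838 = 0.16, in line with the simulation. Intermediate reverse cases at n=60 (Y → M of 0.39 throughout) give 42% (direct drug effects 0.14 on the circuit, 0.39 on impulsivity), 63% (0.39 and zero) and 79% (0.39 on both).

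**Step 4. With the SAP's gate.** Mediation is examined only where path a is significant. Given that, the outcome depends mainly on path b, and the within-arm correlation is 0.36 in all four linked cases. One run gives a × b significant in 80% (forward), 79% (matched reverse), 80% (common cause) and 75% (pure chain) of gated trials at n=60; another puts all four within 76–82%. At n=30 the figures are 49%, 46%, 47% and 44%. The pure-chain figure is the least precise, because only about 19% of its trials pass the gate at n=60.

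**The case against.** The strongest reply is that this limitation belongs to any randomised trial that measures mediator and outcome only before and after treatment, and that the equal rates in Step 3 follow from fixing the drug effect on the circuit and the within-arm correlation. Both statements are true. The simulation illustrates an identity; it does not measure how likely the alternatives are in this trial.

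A reader might infer that the test is significant equally often whatever the direction of effect. The calculations do not support that. Without the gate, the reverse-direction rate runs from about 13% to 79% at n=60, depending on how far the drug moves the circuit directly.

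The wording is also uneven. The protocol sentence is a goal to test something, the formal Aim and Hypotheses 1a and 1b make no mediation claim, and the Lay Summary is hedged. Nothing states that a significant interval will be published as proof of mechanism. The SAP adjusts for baseline impulsivity, and its other-network analysis bears partly on a non-specific brain change.

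The core point survives. The other-network check addresses specificity, not direction or an unmeasured common cause of the target circuit and impulsivity. The SAP's mediation sentence commits to a causal finding under the primary objective, and calling the method standard does not supply the missing property.

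**Conclusion.** The concern holds in conditional form. A significant a × b would show a randomised LDX-versus-GXR difference in circuit change and a within-arm association between circuit change and impulsivity change. It would not by itself establish that the first causes the second.

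Where the drug contrast also moves the circuit by a comparable amount, the test has essentially no power to discriminate between the three explanations. In a pure reverse chain it is significant far less often overall, though still above the 5% seen with no link, and the gate removes most of that protection.

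The percentages rest on the assumed medium effects, the two-sided 5% level, normal errors and complete data. The equality between the forward and matched reverse models does not depend on the size of the effects; it holds for any linear-normal forward model. The documents do not support a stronger conclusion, such as that the mediation analysis is invalid or that impulsivity does drive the circuits.

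**What to change.** 1. **Wording.** In the protocol's Background and the SAP's mediation section, describe path b as an association between circuit change and impulsivity change within treatment groups. Limit the primary conclusion to the randomised LDX-versus-GXR difference in circuit change, plus an association consistent with mediation if there is no unmeasured mediator-outcome confounding and no reverse effect.

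2. **Sensitivity analysis.** Prespecify the residual mediator-outcome correlation at which the indirect effect reaches zero. In these linear models without an interaction it is the partial correlation of the two changes given arm and baseline impulsivity, 0.36 under the assumptions above. The reverse-order model may be shown beside it as illustration only, since the data cannot choose between the two.

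A later parent rating might look like a cure, since under Future Research "we may ask parents/guardians and participants to complete an additional rating scale or brief neuropsychological assessment". It is not recommended. It would fall after the trial, when medication is free for one month and referral is under way, so it would mix in post-trial care. It would also leave common causes untouched.

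The cost is a more modest mechanistic claim and a little more analysis on data already planned. No visit, treatment or clinical rule changes.
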